1.1. Design

The proposed study is a parallel two-group randomized controlled trial in which 120 incarcerated men and 120 incarcerated women will be randomly assigned within gender, to one of two conditions: (1) **XR-NTX+ MMTx**. One injection of XR-NTX in prison followed by 6 monthly injections post-release at the participants's place of residence utilizing mobile medical treatment; or, (2) **XR-NTX-OTx**. One injection of XR-NTX in prison, followed by 6 monthly injections post-release at a community opioid treatment program. All participants will be confirmed opiate-free prior to XR-NTX injection, and evaluated at 1-, 2-, 3-, 4-, 5-, 6-, 7- (safety visit) and 12-months after release from prison.

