2.7.3. A Phase 4, Pilot, Open-label Study of VIVITROL® in the Prevention of Re-arrest and Re-incarceration. This was a Phase 4B, open-label, longitudinal, single cohort, pre-post study. Pre-release opioid-dependent inmates from four Maryland area prisons (three for men and one for women) receive one injection of XR-NTX prior to release from prison and are then offered six monthly injections of XR-NTX for six months post-release. Following prison release, participants were seen for study visits and receive XR-NTX at Glenwood Life Counseling Center in Baltimore, MD. Participants were assessed at 10 time points: at screening (study entry: approximately one month prior to release from prison), at baseline (approximately 1 week prior to release), and then monthly for 6 treatment visits, an end-of-treatment visit, and a safety follow-up visit following their release from prison. We provided XR-NTX to 27 prisoners, of whom 100% received their first injection in prison; 21/27 (77.8%) received their first community injection, 18/27 (67%) received their second community injection; 13/27 (48%) received their third community injection; 11/27 (41%) received their 4th community injection, 10/27 (37%) received their 5th community injection, and 10/27 (37%) received their 6th community injection. Over the one-year enrollment period in this study, 97 individuals were screened for interest; 23 were initially not eligible, and 74 consented. Of these 74, 9 refused, 6 were released early and/or transferred to other prisons; 2 failed to meet the OUD criteria and 3 were positive for buprenorphine (all would have been ineligible for the presently proposed study). Fifteen inmates were excluded for medical reasons, 7 for psychiatric reasons and 5 for both psychiatric and medical reasons. According to the study physician and Co-I on the proposed study, [name], most, if not all, of these 27 excluded for medical and/or psychiatric reasons would have been eligible for the presently proposed study, as the proposed study would not exclude individuals with appropriately treated medical and/or psychiatric conditions. Results indicate participants completing 6 compared to participants completing less than 6 injections were less likely to test positive for opioids in the community (0% vs. 63%, respectively; $p=.003$). Although not statistically significant, individuals who did not complete all 6 injections were more likely to be re-arrested compared to those completing all 6 community injections (31% vs. 0%, respectively; $p=.12$).¹² The limitations of this study included a small sample size which was highly selective and lack of a comparator group. Finally, because the rather long list of exclusion criteria were mandated by the funding agency, the ability to generalize results is limited. The proposed study will have a larger sample size, comparator group, and less stringent exclusion criteria.

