4.0. APPROACH

4.1. Study Overview

This proposed five-year study will focus on whether the addition of mobile medical XR-NTX treatment will increase adherence and thus efficacy of the medication for pre-release prisoners. Project implementation will occur at four pre-release prisons: 1) Brockbridge Correctional Facility (BCF); 2) Dorsey Run Correctional Facility (DRCF); 3) Baltimore City Correctional Center (BCCC); 4) Maryland Correctional Institution (MCIW) for Women; 5) Central Maryland Correctional Facility (CMCF); 6) Maryland Correctional Training Center (MCTC); and 7) Roxbury Correctional Institution (see Maryland Department of Public Safety and Correctional Services **Letter of Support**). Two of these Maryland prisons were sites in our recently completed XR-NTX pilot study (see Research Strategy, above). Following initial screening, informed consent, and medical examination, consenting prisoners at each facility will be block randomized within gender, to either: (See **Figure 1** below): **XR-NTX-OTx**: One injection of XR-NTX in prison, followed by six monthly injections in the community post-

release at an opioid treatment program; or **XR-NTX+MMTx**: One injection of XR-NTX in prison, followed by six monthly injections in the community post-release at the participant's place of residence. All participants will be confirmed opiate-free by urine (all participants will receive two urine drug screens after consent) test and negative naloxone and oral naltrexone tests, and evaluated monthly for 7 months with follow up at 1-, 2-, 3-, 4-, 5-, 6-, 7- (safety visit) and 12-months after release from prison. We consider the proposed follow-up schedule advantageous from both a treatment and research perspective. Regarding treatment, it allows for quicker "rescue" for those overdue for XR-NTX injections. Concerning research, it enables us to stay in closer contact with participants and enhances post-release follow-up assessment completion rates, leading to greater generalizability of findings. The proposed study has two specific aims: **Aim 1**. To compare the two study conditions in terms of: (a) XR-NTX treatment adherence; (b) opioid use; (c) criminal activity; (d) re-arrest; (e) re-incarceration; and (f) HIV risk-behaviors (i. needle use; ii. risky sexual behaviors). **Aim 2**. To determine if the number of months of post-release XR-NTX treatment is related to outcome (a)-(f), and if so, is there a point at which XR-NTX v. Non-XR-NTX equilibrates.

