5.0 SPECIFIC APPROACH

5.1. Maryland Department of Public Safety and Correctional Services (MDPSCS)

Male and female inmates recruited for participation will be drawn from the following seven prisons: 1) Brockbridge Correctional Facility (BCF); 2) Dorsey Run Correctional Facility (DRCF); 3) Baltimore City Correctional Center (BCCC); 4) Maryland Correctional Institution (MCIW) for Women; 5) Central Maryland Correctional Facility (CMCF) 6) Maryland Correctional Training Center (MCTC); and 7) Roxbury Correctional Institution (See **Letter of Support** from MDPSCS). The seven facilities are administered by the Maryland Division Department of Correction (DOC), and are staffed by administrative and custodial personnel and by case managers, who provide referral services and are responsible for preparing reports concerning inmates' institutional progress and adjustment. MDPSCS and FRI investigators have an extensive history of collaborating on pharmacotherapy studies for opioid-dependent prisoners.

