5.2. Participant Eligibility: Inclusion/Exclusion Criteria

Eligible inmates must meet the following criteria: (1) adult male or female inmate at BCF, DRCF, BCCC, MCIW, CMCF, MCTC, or RCI and be eligible for release within 30 days; (2) history of opiate disorder [meeting DSM-V criteria of dependence at the time of incarceration; individuals who do not meet criteria at time of incarceration and become addicted during incarceration will be eligible]; Inmates not meeting the opioid-dependence criterion will be eligible if they were treated in an opioid agonist treatment program during the year before incarceration. (3) suitability for XR-NTX treatment as determined by medical evaluation; (4) currently opioid-free by history, with negative urine for all opioids and no signs of opiate withdrawal; (5) willingness to enroll in XR-NTX treatment in prison [not currently in or planning to pursue agonist (methadone, buprenorphine) treatment at release]; and (6) planning to live in Baltimore City or County (individuals outside of Baltimore City/county will be allowed to participate as long as they agree to travel to the treatment clinic if randomized to OTX). Inmates with one or more of the following conditions will be excluded from the study: (1) Liver function test levels greater than three times normal (note: if a blood specimen is unable to be drawn the individual will not be excluded from participation); (2) Active medical illness that may make participation hazardous (e.g., unstable diabetes, heart disease). Adequately treated medical conditions are acceptable; (3) Untreated psychiatric disorder that may make participation hazardous (e.g., untreated psychosis, bipolar disorder with mania). Adequately treated psychiatric disorders and appropriate psychotropic medications will be allowed; (4) History of allergic reaction to XR-NTX; (5) Current chronic pain diagnosis for which opioids are

prescribed; (6) creatinine above normal limits; (7) pregnancy (for women); (8) Breast-feeding (for women) (9) suicidal ideation (within the past 6-months); and (10) Body Mass Index (BMI) > 40.

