6.4. Explanatory Variables. The predictor variables in all statistical models can be categorized as either Treatment Variables, Covariates, or Control Variables. (From a statistical viewpoint, this categorization is arbitrary and is utilized here simply for ease of presentation.)

Treatment Variables. There will be a single treatment variable: Treatment Condition (XR-NTX-MMTx v. XR-NTX+OTx).

6.4.1. Covariates. Three additional predictor variables – Age, Gender, and age of onset of criminal activity – will be included as “main effects” in all analyses. These “main effects” test for the unique contribution of each of these variables in predicting outcome, above and beyond the effects of Treatment Condition. Each of these variables, as well as its respective interaction with Treatment Condition, will be included as a predictor in order to examine for potential differences in treatment outcome as a function of each covariate, and whether any of these three covariates moderate treatment efficacy.

6.4.2. Control Variables. Finally, because participants may know one another through contact at their respective prison, it is possible that participants' responses within a given prison will not be entirely independent of each other. This potential lack of independence must be controlled for by including Prison nested within Treatment Condition and Participants nested within Prison nested with Treatment Condition as random factors. [Although neither of these two effects represents a substantive effect of interest, both must be included in order to produce unbiased estimates and tests of significance for Treatment Condition.]

6.4.3. Time. Finally, the “repeated factor” in the statistical analysis of all outcome variables measured repeatedly will be assessment Time point, which will allow for the evaluation of both *differential course and impact* of the interventions as a function of the “between-subjects” Treatment Condition factor. (For information regarding which outcome variables are measured at what assessment time points, see **Figure 2**, above.)

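### If all women come from the one prison labelled for women, gender cannot be separated from facility, yet every model tests gender's own contribution and whether gender moderates the effect

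*Combined protocol and SAP*

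**What the plan says.** Section 1.1 plans that "120 incarcerated men and 120 incarcerated women will be randomly assigned within gender"; section 5.4 makes this 60 men and 60 women per arm. Section 5.1 lists seven prisons, of which one carries a sex label: "4) Maryland Correctional Institution (MCIW) for Women".

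Section 6.4.1 enters Age, Gender and age of onset of criminal activity, and the interaction of each with Treatment Condition, in all analyses. The main effects are said to "test for the unique contribution of each of these variables in predicting outcome, above and beyond the effects of Treatment Condition", and the interactions are to show "whether any of these three covariates moderate treatment efficacy".

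Section 6.4.2 expects that participants' "responses within a given prison will not be entirely independent of each other" and adds Prison, nested within Treatment Condition, as a random factor. Section 6.5 says that for outcomes measured once the mixed model reduces to a generalized linear model. It does not say whether the Prison term is kept. Nowhere does the plan link Gender to Prison or limit how a gender result may be read.

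**The concern.** If every woman is at MCIW and every man elsewhere, the Gender coefficient compares one facility with six others. Gender x Treatment compares the mobile effect at MCIW with the mobile effect at the other sites. Release practice, services or catchment at that one prison would be carried by a coefficient labelled gender. The equal split of men and women and the built-in interaction invite a statement on whether mobile delivery works differently for women, and that statement would rest on a single facility.

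A second problem concerns the main-effect test only. MCIW appears in both arms, so nesting Prison within Treatment Condition treats it as two independent prisons. That understates the uncertainty of the gender contrast.

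**Working it through.** **The plan's own figures.** There is none for Gender and none for between-prison variance. The nearest is section 6.7's f² = .037 for a one-degree-of-freedom treatment effect (N = 216, α = .05, power .80). A noncentral F with 1 and 214 degrees of freedom gives f² = .0367 or .0370, depending on whether the noncentrality is f² x 216 or f² x 214. It reproduces, but it does not bear on gender.

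**Inputs.** From the documents: seven prisons, one labelled for women; 120 women and 120 men; 60 of each per arm. Assumed, because the documents are silent: all women at MCIW, 20 men at each of the other six prisons (10 per arm), one normal outcome per person with total variance 1, and a prison intraclass correlation (ICC) of .01 to .10.

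**Aliasing.** The seven Prison indicator columns have rank 7, and still 7 after Gender is added. The Prison x Treatment columns have rank 14, and still 14 after Gender and Gender x Treatment are added. With Prison and Treatment main effects only, adding Gender x Treatment raises the rank from 8 to 9. So a plain facility difference is not aliased with the interaction, but a facility difference in the treatment effect is.

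**Variance of the gender contrast.**
- Prison ignored: 2/120, SE = .129 SD.
- Prison counted once: ICC x (1 + 1/6) + (1 - ICC) x 2/120. At ICC .05 this is .0583 + .0158 = .0742, SE = .272.
- As the nested term implies: ICC x (1/2 + 1/12) + (1 - ICC) x 2/120. At ICC .05 this is .0292 + .0158 = .0450, SE = .212.

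With the variances known, the nested test at ICC .05 has an effective critical value of 1.96 x .212/.272 = 1.53 and a false-positive rate of .127. Across the four ICCs the rate is .081/.100/.127/.144. Estimating the variance from few units adds to this, as the simulated REML rates in the table show (no true gender effect, prison effect common to both arms).

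| Assumed ICC | .01 | .02 | .05 | .10 |
|---|---|---|---|---|
| SE, prison counted once | .168 | .199 | .272 | .363 |
| SE implied by nesting | .149 | .167 | .212 | .271 |
| Gender rejections: as planned, normal reference | .09 | .12 | .18 | .22 |
| As planned, t with 10 df (14 cells - 4 fixed effects) | .05 | .09 | .14 | .18 |
| Prison not nested, normal reference | .08 | .11 | .15 | .14 |
| Prison not nested, t with 5 df (7 prisons - 2) | .03 | .04 | .07 | .09 |
| No Prison term | .16 | .21 | .33 | .52 |

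Separate simulation runs agree to within a few hundredths. More women at the same prison cannot bring the SE below √(ICC x 7/6), which is .108/.153/.242/.342. Power for a true gender difference of 0.5 SD (normal reference) is .97 if prison is ignored and .85/.71/.45/.28 once it is counted.

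**Moderation.** Under the same truth, Gender x Treatment rejects in .01 to .03 of trials with the planned model, below nominal. If the mobile effect itself varies between facilities (assumed variance .04 with ICC .02, or .10 with ICC .05), the planned model rejects in about .08. A non-nested Prison intercept (normal reference) rejects in .14 and .26.

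**The case against.** The premise is inferred. No section says that the other six prisons hold only men, and section 5.2 admits any "adult male or female inmate at BCF, DRCF, BCCC, MCIW, CMCF, MCTC, or RCI". That is one pooled list, though, and does not say that any site is mixed. The same team's pilot (section 2.7.3) used "four Maryland area prisons (three for men and one for women"), but section 4.1 says only that "Two of these Maryland prisons were sites in our recently completed XR-NTX pilot study" and does not say which two. The inference is strong, but the point has to stay conditional.

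The plan's wording claims a contribution beyond Treatment Condition, not beyond Prison, and no aim or hypothesis concerns gender. That stands. It confines the issue to the reading of a covariate and a subgroup result.

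Four stronger readings are tempting and are not supported:
- *Any facility difference will be reported as a gender effect.* Prison is in the model as a random factor, so the excess is partial. At ICC .01 with 10 df it is absent.
- *All the gender tests exceed their error rate.* The interaction test does not when the facility difference is common to both arms, because women are randomised to both arms within the same facility.
- *No model can control the error rate.* A non-nested Prison term with 5 df comes close to nominal. It cannot supply attribution: it assumes that MCIW's facility effect comes from the same distribution as the other six, and one women's prison cannot test that.
- *The treatment comparison is biased.* Randomisation is within gender, so it is not.

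**Conclusion.** The point holds conditionally. If women come only from MCIW, neither the Gender main effect nor Gender x Treatment can be attributed to gender rather than to that facility, whichever model is fitted. For the main effect there is also an error-rate problem under the planned nesting: roughly .05 to .18 with 10 df, or .09 to .22 with a normal reference, over ICC .01 to .10. It would be larger if the Prison term were dropped for outcomes measured once. For moderation the problem is attribution alone: a facility difference in the mobile effect would be read as a gender difference.

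The sizes rest on assumed ICCs, an even spread of men over six prisons and a single normal outcome. The attribution argument rests only on where the women are recruited. Secondary conclusions are affected; the main randomised comparison is not.

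**What to change.** 1. State the sex of inmates housed at each of the seven sites.
2. Keep Gender, the randomisation stratum, and Gender x Treatment in the models, but delete for Gender the claim that its main effect shows a unique contribution.
3. Enter Prison as a random factor not nested in Treatment Condition, with small-sample degrees of freedom. Both parts are needed: with a normal reference, removing the nesting alone still leaves .08/.11/.15/.14. Say whether the term is kept for outcomes measured once.
4. If women come only from MCIW, report the gender main effect and the interaction, with confidence intervals, as an exploratory contrast of women's facility v. men's facilities. State that gender and facility cannot be separated in this design.

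The cost is analysis-plan wording, the loss of a stand-alone gender claim, and an interval for the gender contrast built on an SE of about .17/.20/.27/.36 SD rather than .13. A non-nested Prison intercept also gives the interaction test less protection if the mobile effect varies by facility (.14 to .26 against about .08), which is a further reason for the exploratory label.

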5.4. Random Assignment Procedure

Participants will be assigned to one of two conditions (**XR-NTX-MMTx** or **XR-NTX+OTx**) using a random permutation procedure, such that, within gender for each block of 2, 4, or 6 participants, half will be assigned at random to the XR-NTX-MMTx Condition [$n=120$: 60 men, 60 women] and half to the XR-NTX+OTx condition [$n=120$: 60 men, 60 women], ensuring that both male and female participants have an equal chance of being assigned to either condition.⁸⁵ [Random block sizes will be used in order to conceal allocation to treatment condition. Sealed envelopes will be prepared for the study physician based on this block randomization procedure so that he can explain the condition to which a participant has been assigned. He will open the designated envelope and inform the participant to which one of the two conditions s/he has been assigned. This assignment procedure will be performed by the study physician so that, immediately after assignment to treatment condition, consent to medication initiation can be obtained from participants.

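### Prison is modelled as nested within treatment although both arms are randomised in the same prisons; for normal repeated outcomes this widens time-averaged intervals unless effects differ by prison

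*Combined protocol and SAP*

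**What the plan says.** Section 6.4.2 (Control Variables) is concerned that participants from one prison may know each other and so not respond independently. It deals with this by "including Prison nested within Treatment Condition and Participants nested within Prison nested with Treatment Condition as random factors", and adds that "both must be included in order to produce unbiased estimates and tests of significance for Treatment Condition". Section 6 contains no prison term shared by the two arms.

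The design sections describe individual randomisation inside common facilities:

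- Section 4.1: "consenting prisoners at each facility will be block randomized within gender".
- Section 5.1: "Male and female inmates recruited for participation will be drawn from the following seven prisons". One of these is listed as "Maryland Correctional Institution (MCIW) for Women".
- Section 5.4: "within gender for each block of 2, 4, or 6 participants, half will be assigned at random". Gender is the only stratum named there.
- Section 1.1: "120 incarcerated men and 120 incarcerated women will be randomly assigned within gender".

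Section 6.4.1 adds Age, Gender and age of onset of criminal activity to every model: "Each of these variables, as well as its respective interaction with Treatment Condition, will be included as a predictor".

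**The concern.** Nesting prison within treatment means that each prison belongs to one arm, as in a cluster-randomised trial. Here both arms are expected in every prison. The nested model gives each prison two unrelated effects, one per arm, or 14 clusters in place of 7.

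Two things follow. First, prisoners who share a facility but are in different arms are modelled as independent, although their possible dependence is the reason given for the term. Second, a prison effect common to both arms largely cancels from the treatment contrast, but the nested model charges it to the error. The single nested variance also cannot separate variation between prisons from variation between prisons in the treatment effect.

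At stake is precision. Section 6.1 commits to confidence intervals, and section 5.9.2 expects mobile treatment to be superior. Needlessly wide intervals could hide a real benefit.

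**Working it through.** **1. The plan's own figure.** Section 6.7 gives power .80 at f² = .037, alpha = .05, N = 216 for a treatment main effect without Time. Noncentral F on 1 and 214 df with λ = .037 × 216 = 7.99 gives .804, so the figure reproduces. It contains no prison variance. In standardised units, d = 2√.037 = .385.

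**2. Inputs.** From the documents: N = 240 × .9 = 216, so 108 per arm; seven prisons; equal numbers of men and women, so 108 of each and 54 per arm within gender. Assumed: total variance 1, prison ICC ρ = .01, .02 or .05, no prison-by-treatment interaction, arms balanced within prison. Two layouts: seven equal prisons; or one prison supplying all women and six equal prisons supplying the men, with the effect averaged over gender. The documents do not say whether other sites supply women.

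**3. Variance of the time-averaged treatment contrast, normal outcome.**

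- Crossed: V = 2(1 − ρ)/108.
- Nested, seven equal prisons: V + 2ρ/7.
- Nested, one women's prison: ¼[2(ρ/6 + (1 − ρ)/54) + 2(ρ + (1 − ρ)/54)].

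At ρ = .02: crossed 2 × .98/108 = .01815; equal prisons .01815 + .00571 = .02386, ratio 1.31; one women's prison .02981, ratio 1.64. Interval width follows the square root of the ratio.

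| ρ (assumed) | Crossed | Nested, 7 equal | Ratio | Wider by | Nested, 1 women's prison | Ratio | Wider by |
|---|---|---|---|---|---|---|---|
| .01 | .01833 | .02119 | 1.16 | 8% | .02417 | 1.32 | 15% |
| .02 | .01815 | .02386 | 1.31 | 15% | .02981 | 1.64 | 28% |
| .05 | .01759 | .03188 | 1.81 | 35% | .04676 | 2.66 | 63% |

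In the one-women's-prison layout the Gender x Treatment contrast has four times both variances, so the same ratios apply.

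**4. Type I error, normal outcome, no interaction.** REML simulation, 4,000 replicates per cell, residual df, nominal .05, Monte Carlo error about ±.007, ρ = .01/.02/.05:

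- Seven equal prisons: nested .031/.031/.021; shared intercept .046/.051/.060.
- One women's prison: nested .029/.024/.021; shared intercept .048/.045/.058.

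The df rule matters. In a second simulation (1,500 to 3,000 replicates) with df based on the prison-by-arm cells, nested type I error at ρ = .02/.05 was .017/.012 (equal prisons, 12 df) and .011/.006 (one women's prison, 10 df). The plan states no df rule.

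**5. Binomial outcome.** Count of six injections, maximum likelihood, assumed participant SD of 2 on the logit scale, 500 replicates, Monte Carlo error about ±.02, ρ = .02/.05:

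- Seven equal prisons: variance ratio 1.22/1.42; type I error nested .032/.024, shared .042/.050.
- One women's prison: variance ratio 1.05/1.17; type I error nested .064/.052, shared .066/.058.

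The second layout shows no clear conservatism. Poisson outcomes were not computed.

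**6. Half of the prison variance is interaction.** Normal outcome, type I error at ρ = .01/.02/.05:

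| Model | 7 equal | 1 women's prison |
|---|---|---|
| Nested | .046/.043/.044 | .045/.045/.066 |
| Shared intercept only | .062/.071/.100 | .075/.085/.152 |
| Shared intercept plus random prison-by-treatment, 6 or 5 df | .021/.018/.025 | .016/.014/.035 |

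**7. Parts of the plan not reached.** A prison intercept that is constant over time cancels within person, so Treatment x Time on the linear scale does not carry it. For outcomes measured once at the end, section 6.5 reduces the model to a generalised linear model, which has no random effects.

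**The case against.** The strongest reply is that the nested term errs on the safe side and the replacement may not. Step 6 bears this out: with half of the prison variance as interaction, the nested test is close to nominal, while a shared intercept alone rejects too often. This stands. It is why the shared-intercept model should not be reported without a prison-by-treatment sensitivity analysis. It does not rescue the nested term, which cannot show which situation holds.

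A second reply is that the larger figures come from a normal model, whereas section 6.3 treats adherence and urine screens as binomial and days of crime as Poisson. This also stands. A reader might infer that the adherence comparison loses 15 to 63% in interval width; neither the plan's distributional assumptions nor step 5 supports that.

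Third, the ICC, prison sizes, share of interaction and source of the women are all assumptions. The size therefore is uncertain, but the mismatch between sections 4.1 and 6.4.2 needs none of them.

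Finally, the bracketed sentence in 6.4.2 covers two terms, and one might conclude that it is wrong throughout. It is not: the random participant term is needed for valid tests on repeated outcomes. Only the claim about nesting prison within treatment fails.

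**Conclusion.** The specification contradicts the design: prison is crossed with treatment but is modelled as nested. For normally distributed repeated outcomes without prison-by-treatment interaction, time-averaged treatment tests are conservative, to the extent shown in step 3 under the assumed ICCs and layouts. For binomial outcomes the effect is smaller and uncertain (variance ratio 1.05 to 1.42), and for Poisson outcomes it is unknown.

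Two stronger conclusions are tempting and unsupported. One is that the treatment estimate is biased or that a false benefit could arise: individual 1:1 randomisation protects the estimate, and when effects do not differ by prison the normal-outcome error is towards missing a benefit. The other is that the power figures in section 6.7 are wrong: .81 to .85 is for Treatment x Time, and .80 at f² = .037 is for models without Time, such as reincarceration. Neither is shown to depend on the nested prison term.

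Importance is minor to moderate. The structural point is firm; its size is not.

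**What to change.** In section 6.4.2:

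- Replace the nested prison term with a random prison intercept shared by both arms (crossed with Treatment Condition), keep the random participant term within prison, and state the df method.
- Keep prison random. If one facility supplies all women, fixed prison effects would be collinear with the Gender main effect that 6.4.1 requires.
- Prespecify one sensitivity analysis that adds a random prison-by-treatment term, tested on prison-level df (5 or 6 with seven prisons), and report its interval beside the main one.
- Reword the bracketed sentence to say that the participant term is needed for valid tests on repeated outcomes, and remove the claim that nesting prison within treatment is required for unbiased estimates and tests.

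The cost is SAP wording, one changed model statement and one added model; no new data are needed. The main model then relies on there being no large prison-by-treatment variation. The sensitivity model checks this at lower power: about .47 to .61 at d = .385, where the main model has about .80 to .83 (no interaction, ICC 0 to .05). The choice should be fixed before outcomes are seen by arm, because it changes interval width.
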